7.5.3.2 Follow-Up Therapy

The following information pertaining to subsequent therapies will be summarized:

Number and percentage of participants receiving subsequent therapies including:

- Chemotherapy by drug name.
- Immunotherapy (anti-PD1 agents, anti-CTLA4 agents and others, by drug name).
- Brentuximab
- Other investigational agent by drug name.
- Transplant/Surgery.
- Radiotherapy.
- Any combination of the above.

A participant listing of follow-up therapy will be produced for participants who had any subsequent therapy.

7.5.4 Interim Analysis

An independent statistician external to BMS will perform the analysis. In addition to the formal planned analysis on CRR and interim analysis for PFS, the DMC will have access to periodic unblinded interim reports of efficacy and safety to allow a risk/benefit assessment. Details are included in the DMC charter.

A formal interim analysis for superiority of PFS in participants randomized to receive nivolumab+BV vs. participants randomized to receive BV will be performed on all randomized participants when at least 131 PFS events have been observed (approximately 70% (131/187) of the total number of events required for the final PFS analysis).

This PFS comparison will be tested using the interim monitoring feature of East software (version 6.3) based on a generalization of the Lan-DeMets error spending function approach using an O'Brien-Fleming stopping boundary⁹ to reject H_0 , (H_0 = no treatment difference) controlling for a two-sided overall alpha of 5.0%. For example, if exactly 131 PFS events were in the locked database for the interim analysis, H_0 would be rejected at the interim if the p-value from the stratified log-rank test is $p < 0.0148$. If the study continues beyond the interim look, H_0 would be rejected at the final PFS analysis if the p-value from the stratified log-rank test is $p < 0.0455$.

If the number of PFS events is not exactly 131 at the time of the interim analysis, the nominal critical points and values for interim and final analyses will be calculated based upon the observed information fraction (number of events at the interim over the planned 187 events at the final).

A hierarchical testing procedure is employed to control the study-wise type I error at 5% level. Specifically, only if the primary PFS analysis result is significant at either interim or final analyses, the comparison of CRR between two treatment arms will be performed at an alpha level of 5%. Otherwise, CRR will not be compared between two arms, and consequently the p-value will not be reported for CRR. In that case, only CRR in both treatment arms will be reported with 95% CI.

The DMC will review the safety and efficacy data from the interim analyses and will recommend if the study should continue with or without changes or if accrual should be stopped. Participant enrollment will continue while waiting for the DMC's decisions. More details of the interim analyses are discussed in the Data Monitoring Committee Charter.

The chair of the DMC and the sponsor can call an unscheduled review of the safety data.

Implications of PFS Interim Analysis

At the time of the formal interim analysis for superiority of PFS, the DMC may recommend continuing or stopping the trial.

If the trial continues beyond the interim look, the nominal critical point for the final PFS analysis will be determined using the recalculated information fraction at the time of the interim analysis, as described above. The final PFS hazard ratio and corresponding confidence interval will be reported whereby the confidence interval will be adjusted accordingly (i.e. using the recalculated nominal α level at the final analysis)..

If the trial is stopped for superiority of PFS at the interim, the p-value from the interim stratified log-rank test will be considered the final primary PFS analysis result. The p-values from these analyses will be considered as the final results.

7.6 Safety

7.6.1 Deaths

See Core Safety SAP.

7.6.2 Serious Adverse Events

See Core Safety SAP.

7.6.3 Adverse Events Leading to Discontinuation of Study Therapy

See Core Safety SAP.

7.6.4 Adverse Events Leading to Dose Delay of Study Therapy

See Core Safety SAP.

7.6.5 Adverse Events

See Core Safety SAP.

7.6.6 Multiple Events

See Core Safety SAP.

7.6.7 Select Adverse Events

See Core Safety SAP.

7.6.8 Clinical laboratory evaluations

The analysis population for each laboratory test is restricted to treated participants who underwent that laboratory test.

7.6.8.1 Hematology

See Core Safety SAP.

7.6.8.2 Serum Chemistry

See Core Safety SAP.

[figure not shown]
7.6.9 Vital Signs and Pulse Oximetry

[figure not shown]
See Core Safety SAP.

[figure not shown]

[figure not shown]
7.6.11 Pregnancy

See Core Safety SAP.

8 CONVENTIONS

The following conventions may be used for imputing partial dates for analyses requiring dates:

For missing and partial adverse event onset dates, imputation will be performed using the Adverse Event Domain Requirements Specification¹⁰. Missing and partial Non-Study Medication Domain dates will be imputed using the derivation algorithm described in BMS Non-Study Medication Domain Requirements Specification¹¹.

For death dates, the following conventions will be used for imputing partial dates:

If only the day of the month is missing, the 1st of the month will be used to replace the missing day. The imputed date will be compared to the last known alive date and the maximum will be considered as the death date.

- If the month or the year is missing, the death date will be imputed as the last known alive date.
- If the date is completely missing but the reason for death is present the death date will be imputed as the last known alive date.

For date of progression, the following conventions will be used for imputing partial dates:

- If only the day of the month is missing, the 1st of the month will be used to replace the missing day.
- If the day and month are missing or a date is completely missing, it will be considered as missing.

- In case, the date of death is present and complete, the imputed progression date will be compared to the date of death. The minimum of the imputed progression date and date of death will be considered as the date of progression.

For other partial/missing dates, the following conventions will be used:

- If only the day of the month is missing, the 15th of the month will be used to replace the missing day.
- If both the day and the month are missing, “July 1” will be used to replace the missing information.
- If a date is completely missing, it will be considered as missing.

The following conversion factors will be used to convert days to months or years:

$$1 \text{ month} = 30.4375 \text{ days and } 1 \text{ year} = 365.25 \text{ days}$$

Duration (e.g. time from first diagnosis of RCC to first dosing date, duration response, and time to response) will be calculated as follows:

$$\text{Duration} = (\text{Last date} - \text{first date} + 1)$$

All statistical analyses will be carried out using SAS (Statistical Analysis System software, SAS Institute, North Carolina, USA) unless otherwise noted.

[figure not shown]
Safety conventions from Programming may be summarized separately in an appendix.

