### **8.3 Lost to Follow-Up**

- All reasonable efforts must be made to locate participants to determine and report their ongoing status. This includes follow-up with persons authorized by the participant.
- Lost to follow-up is defined by the inability to reach the participant after a minimum of **three** documented phone calls, faxes, or emails as well as lack of response by participant to one registered mail letter. All attempts should be documented in the participant's medical records.
- If it is determined that the participant has died, the site will use permissible local methods to obtain date and cause of death.
- If investigator's use of third-party representative to assist in the follow-up portion of the study has been included in the participant's informed consent, then the investigator may use a Sponsor retained third-party representative to assist site staff with obtaining participant's contact information or other public vital status data necessary to complete the follow-up portion of the study.
- The site staff and representative will consult publicly available sources, such as public health registries and databases, in order to obtain updated contact information.
- If after all attempts, the participant remains lost to follow-up, then the last known alive date as determined by the investigator should be reported and documented in the participant's medical records.

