4 ENDPOINTS

4.1 Primary Endpoints

Progression Free Survival (PFS)

Progression-free Survival (PFS) by BICR: defined as time from date of randomization to the date of death due to any cause or the first documented disease progression as determined by the BICR, whichever occurs first.

Participants who die without a reported progression will be considered to have progressed on the date of their death. Participants who did not progress or die will be censored on the date of their last tumor assessment. Participants who did not have any on study assessments and did not die will be censored on the randomization date. A participant who initiates a subsequent anti-cancer therapy (including allogeneic transplant) will be censored on the date of last tumor assessment prior or on the start date of their subsequent anti-cancer therapy.

The censoring scheme is summarized in Table 4.1-1.

Table 4.1-1: Censoring scheme used in primary analysis of PFS

Situation	Date of Progression or Censoring	Outcome
No baseline tumor assessments	Randomization date	Censored

No on-study tumor assessments and no death	Randomization date	Censored
New subsequent anticancer therapy started without a prior reported progression by BICR or death	Date of last evaluable tumor assessment prior to or on the date of initiation of the subsequent anti-cancer therapy	Censored
Progression per BICR documented at a scheduled or unscheduled visit and no other subsequent anticancer therapy started before	Date of the first documented tumor progression	Progressed
Participant progression free, no death and no subsequent anti-cancer therapy started	Date of last evaluable tumor assessment	Censored
Death without prior progression per BICR and no subsequent anticancer therapy started	Date of death	Progressed

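### The partial-date rules in SAP Section 8 can drop or mis-date a PFS or DOR event, and can place a death before its recorded year

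*SAP*

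**What the plan says.** SAP Section 8 introduces its date rules as optional: "The following conventions may be used for imputing partial dates for analyses requiring dates". They differ by type of event.

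- **Progression, day missing:** "If only the day of the month is missing, the 1st of the month will be used to replace the missing day". The only check is against a complete death date: "The minimum of the imputed progression date and date of death will be considered as the date of progression".
- **Progression, day and month missing, or no date:** "If the day and month are missing or a date is completely missing, it will be considered as missing".
- **Death, day missing:** the 1st of the month, then a lower bound: "The imputed date will be compared to the last known alive date and the maximum will be considered as the death date".
- **Death, month or year missing:** "If the month or the year is missing, the death date will be imputed as the last known alive date". A death with no date but a recorded reason is handled the same way.
- **Other dates with only the year known:** 1 July of that year.

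SAP Section 4.1 gives PFS as "defined as time from date of randomization to the date of death due to any cause or the first documented disease progression". Table 4.1-1 dates a progression event at the first documented progression. It censors participants who are progression free and alive, without subsequent therapy, at the last evaluable assessment. It counts a death without prior progression as an event if no subsequent therapy was started. SAP Section 4.2.1 gives DOR and DOCR the same censoring scheme.

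**The concern.** Each rule can produce a result that the recorded data contradict.

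1. A progression known to have happened in a given year loses its date. The SAP does not say whether it still counts as an event. An undated death with a recorded reason does count, so the two components of PFS are treated differently.
2. A day-missing progression is bounded above by death but has no lower bound at randomization, at response or at the last progression-free scan. The day-missing death rule has such a bound.
3. A recorded year of death is ignored once the month is missing.

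At stake are the descriptive PFS, DOR, DOCR and OS estimates. Under the revised protocol, progression is assessed by the investigator and images no longer go to a core lab (Protocol Section 9.1.1). No protocol PET is obtained after a participant stops treatment without progression (Table 2-3), and subsequent therapy may be recorded by phone. Partial dates are therefore possible, although the documents give no frequency.

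**Working it through.** Section 8 states no figure to reproduce. The check applies its rules to constructed dates.

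**Inputs from the documents.** Duration = last date − first date + 1 (SAP Section 8). Scans are every 5 cycles of 21 days, so 5 × 21 = 105 days apart (Protocol Table 2-2 and Section 5.1). Unscheduled scans are allowed when recurrence is suspected (Table 2-2). Randomized: 23 (Protocol Section 10).

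**Assumed for illustration.** Randomization on 10-Jan-2019, and all event dates below.

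**Case 1: progression with only the year.** Clean scan on 25-Apr-2019 (day 106); progression at the next scheduled scan, 8-Aug-2019 (day 211); only 2019 is recorded.
- Alive, no subsequent therapy: the date is missing and no row of Table 4.1-1 fits. The likely outcome is censoring at day 106. One event is lost and follow-up is cut by 211 − 106 = 105 days.
- Death without subsequent therapy: the PFS event is kept but moves later, to the death date.
- With a floor at the day after the clean scan: event at day 107, which is 211 − 107 = 104 days early.
- At the latest date compatible with the record, 31-Dec-2019: event at day 356, which is 356 − 211 = 145 days late.

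**Case 2: progression with the day missing.** Response scan on 5-Aug-2019 (day 208); off-schedule scan shows progression on 28-Aug-2019 (day 231); only August 2019 is recorded.
- As written: progression on 1-Aug-2019, PFS = day 204, before the response scan on day 208.
- DOR = 1-Aug − 5-Aug + 1 = −3 days, against a true 24 days.
- With the floor (6-Aug-2019): PFS = day 209, DOR = 2 days.
- The shift cannot exceed 30 days (31st to 1st). The contradiction needs the clean scan and the progression in one calendar month, which a 105-day interval excludes unless a scan is unscheduled or off schedule.

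**Case 3: death with only the year.** Last known alive 20-Nov-2019; death recorded as 2020.
- As written: OS = 315 days.
- Earliest date compatible with the record (1-Jan-2020): 357 days, so at least 357 − 315 = 42 days short.
- Latest (31-Dec-2020): 722 days, so at most 722 − 315 = 407 days short.
- The death remains an event. The conflict arises only if the last known alive date falls in an earlier year.

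**Scale.** One affected participant is 1/23 = 4.3% of the sample.

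**The case against.** The strongest reply is that these cases should be rare. Progression is judged on imaging, and a scan normally carries a full date (an assumption), so a year-only progression would usually be queried and resolved. Case 2 needs an off-schedule scan. For deaths, the protocol says: "If it is determined that the participant has died, the site will use permissible local methods to obtain date and cause of death". Deaths within the collection period are SAEs reportable within 24 hours, dosing visits are every 3 weeks, and follow-up visits fall 35 and 100 days after the last dose, with survival follow-up ending at the second. A gap near 407 days is therefore theoretical under the current schedule. No formal testing is planned. All of this stands and keeps the point minor. It does not make the rules correct when they are invoked.

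A reader might also infer more than the documents support:

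- **That an undated progression is always lost as an event.** The SAP makes the date missing. Loss of the event is an inference from Table 4.1-1, and it does not follow for PFS when the participant dies without subsequent therapy. An imputed death date may also serve there, because Section 8 imputes partial death dates.
- **That OS loses events.** It does not.
- **That one lost event lifts an arm's Kaplan-Meier curve by a fixed 8 to 9 points (1/12 to 1/11) from then on.** The split by arm is not given, and the gap shrinks. If the first of 12 at risk is censored instead of counted, it is 8.3 points until the next event. With 5 still event-free and no other censoring it is 5/11 − 5/12 = 3.8 points, and it reaches 0 if all progress.

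**Conclusion.** The point holds in conditional form. When partial dates occur, Section 8 can remove a documented progression from PFS and DOR or move it to death. It can also date a progression before a clean or response scan in the same month, or a death before its recorded year. The sizes in the constructed cases are one lost event with 105 days cut from follow-up, at most 30 days for a missing day, and 42 to 407 days of OS.

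Severity is minor. The frequency is unknown, and the effect is limited to descriptive estimates in 23 participants. The conclusion rests on two assumptions: that at least one partial date reaches the final database unresolved, and that an undated progression in a living participant would be programmed as censored, since Table 4.1-1 offers no other fit.

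**What to change.** Amend SAP Section 8, and make its wording binding rather than optional:

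- **Partial progression date:** use the earliest date compatible with the recorded parts, not before the day after the last evaluable progression-free assessment (or randomization if there is none) and not after death.
- **Documented progression without a usable date:** state that it stays an event, by default at that floor. Add the matching row to Table 4.1-1, which DOR and DOCR then inherit.
- **Death with only the year:** the later of 1 January of that year and the last known alive date.
- **Sensitivity display:** repeat the estimate with each such progression at its latest compatible date.

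The last item is needed because the floor can be early by about one 105-day scan interval, and with no prior scan it puts the event at randomization. Early dating lowers the curve of the arm concerned, but it should not be called conservative for the comparison between arms, since its direction depends on which arm has the partial dates.

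The cost is a few sentences and a few lines of derivation code. The SAP is still the initial version of 24-Feb-17 and based on central review, so it needs revision for the amended protocol in any case.

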9 CONTENT OF REPORTS

All analyses describe in this SAP will be included in the final Clinical Study Report. Refer to the Data Presentation Plan for mock-ups of all tables and listings.

11 DOCUMENT HISTORY

Table 11-1: Document History

Version Number	Author(s)	Description
1.0	██████████	Initial version- 24-Feb-17
